3.5. Safety Endpoints

Safety will be assessed by the spontaneous reporting of AEs, physical examinations, and clinical laboratory results in all subjects who receive at least one dose of the investigational product. Unscheduled safety assessments may be performed at any time during the study to assess any perceived safety concerns. Endpoints will be assessed as,

- Treatment-emergent adverse events.
- Treatment-emergent SAEs and AEs leading to discontinuation.
- Clinical abnormalities and change from baseline in selected clinical laboratory values, ECG measurements, and vital signs.

The safety endpoints will be defined in accordance with Clinical Data Interchange Standards Consortium (CDISC) and Pfizer Standards (CaPS).

3.5.1. Adverse Events

An adverse event is considered TEAE to a given treatment if the event started during the effective duration of treatment. All events that start on or after the first dosing day, but before or on the last dosing day plus the lag time (28 days) will be flagged as TEAEs. The algorithm will not consider any events that started prior to the first dose date.

3.5.2. Laboratory Data

Below is a list of hematology and serum chemistry test parameters.

- Hematology: hemoglobin, hematocrit, red blood cell count, reticulocyte count, platelet count, white blood cell count with differential, total neutrophils, eosinophils, monocytes, basophils, lymphocytes, lymphocyte subsets (markers), coagulation panel.
- Serum chemistry: blood urea nitrogen, creatinine, creatine phosphokinase, glucose, sodium, potassium, chloride, calcium, total bicarbonate, aspartate aminotransferase, alanine aminotransferase, *gamma-glutamyl transferase*, bilirubin, alkaline phosphatase, lactate dehydrogenase, uric acid, albumin, total protein, total cholesterol, low-density lipoprotein (LDL), high-density lipoprotein (HDL), triglycerides.

3.5.3. Vital Signs, Including Height and Weight

Vital sign measurements are oral or tympanic temperature, respiratory rate, pulse rate, and blood pressures.

Weight is collected at pre- and post-treatment. Height is not required at the baseline visit. Only adolescents (12 to <18 years old) require repeated height measurement at Screening, Week 12 and End of Treatment (EOT) visits during the double-blind phase. Adults require one height measurement at the Screening visit. See [Appendix 7](#) for further details.

3.5.4. Physical Examinations

Complete physical examinations consist of assessments of general appearance; skin; head, eyes, ears, nose and throat; mouth, heart; lungs; breast (optional); abdomen; external genitalia (optional); extremities; neurologic function; and lymph nodes.

4. ANALYSIS SETS

Data for all subjects will be assessed to determine if subjects meet the criteria for inclusion in each analysis population prior to unblinding and releasing the database and classifications will be documented per standard operating procedures.

4.1. Full Analysis Set (FAS)

The following groups of FAS will be defined for this study:

FAS-OL: This is the set of all subjects who received at least one dose of study treatment during the open label run-in phase. For all analyses, Study Baseline will be used (see [Section 3.4](#)).

FAS-RA: This is the set of all subjects who have been randomized at Week 12 and have received at least one dose of study treatment within the double-blind phase. By study design, this will be a subset of FAS-OL. Subjects are assigned to the randomized treatment group regardless of actual treatment received. All analyses will be reported by treatment

regimen/sequence (eg, OL 200 mg → DB 200 mg or OL 200 mg → DB 100 mg or OL 200 mg → DB Placebo). For analysis purposes, either the Study Baseline or the Randomization Baseline will be used, depending on the endpoint and/or the analysis (see [Sections 3.4 and 6](#)).

FAS-RE: This is the set of all subjects who have met the protocol definition of a flare (see [Section 2.2](#)) during the double-blind phase and have received at least one dose of rescue treatment. By study design, this will be a subset of FAS-RA. In general, for efficacy analyses, Rescue Baseline will be used (see [Section 3.4](#)).

In general, change from baseline analyses based on any of the above FAS groups will require at least one post-baseline observation recorded. Analyses for endpoints that are defined based on a threshold of change from baseline (eg, NRS4) will also require the baseline value to meet that threshold (eg, for NRS4, the baseline value needs to be ≥ 4).

4.2. Per Protocol Analysis Set (PPAS)

The PPAS will be a subset of the FAS-RA consisting of subjects who had no major protocol violations. Subjects excluded from the PPAS will be determined and documented before the study is un-blinded. This set will include subjects who:

- Met key inclusion criteria (ie, IGA ≥ 3 , EASI ≥ 16 at Study Baseline, had documented prior qualifying treatment for AD).
- Met protocol-defined criteria for randomization (ie, responder for both IGA and EASI-75 at Week 12).
- Did not take a protocol-prohibited therapy for the primary diagnosis (ie, high potency or systemic medication or phototherapy) during the initial run-in period and during the randomized withdrawal period.
- Did not take a protocol prohibited (CYP2C19/CYP2C9 inhibitor and/or inducer drug) concomitant medication.
- Had an overall compliance of $\geq 80\%$ but $\leq 120\%$ with randomized study treatment.
- (if not flared), completed the study.
- Had no other major protocol violations that is likely to affect materially the clinical observations, or the outcomes of the subject determined by the clinical team.

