### **9.2.3. Analysis of the Primary and Key Secondary Endpoints**

The primary analyses for both endpoints will be based on the FAS-RA subset. Secondary analyses will be based on the PPAS. For analysis of the primary and key secondary endpoints, a combination of graphical and analytical methods will be used. The time (in weeks) to protocol-defined flare will be used to evaluate the primary endpoint while the time (in weeks) to achieve an IGA score of  $\geq 2$  will be used to evaluate the key secondary endpoint. Subjects who do not report an event (ie protocol-defined flare or IGA  $\geq 2$ ) or discontinue the study during the double-blind randomized period will have their time to event censored at their last known visit in this period. Kaplan-Meier curves will be used to display the time to event and report the median time to event (and its 95% confidence interval) among the three randomized groups. The log-rank test will be used to compare these curves. Proportions of subjects with an event and confidence intervals will also be reported by randomized group.

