3.2. Key Secondary Endpoint

As the key secondary endpoint, loss of response is defined as being no longer able to maintain an IGA score of 0 or 1 (as at randomization) and having an IGA score of ≥ 2 during the randomized, double-blind period.

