5.3.3. Time to Event Endpoints

Subjects who reach the end of their accrual period without experiencing the event of interest will have their event times right censored at the end of their accrual period (ie, administrative censoring). Subjects who permanently discontinue before the end of their accrual period without experiencing the event of interest will have their event times considered missing.

For the primary analysis, these missing event times will be considered as right censored (censored at random) on their last date of dosing. As sensitivity analyses, tipping point analyses will be performed where these missing event times will be multiply imputed under an assumption of censoring not at random as proposed in Atkinson et al. (2019)¹ (see [Appendix 6](#)).

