6.1.1.2. Additional/Supportive Analyses

Additional analysis of the loss of response would be as:

- The time to loss of response will be analyzed using the methods in [Section 5.2.4](#) for the PPAS population.
- Missing time to loss of response will be multiply imputed under censoring not at random under a tipping point analysis framework using the methods in [Section 5.2.4](#) and [Appendix 6](#) for the FAS-RA population.

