6.2.1.2. Additional/Supportive Analyses

Additional analysis of the loss of response based on the IGA score would be as:

- The time to loss of response based on the IGA score will be analyzed using the methods in [Section 5.2.4](#) for the PPAS population.

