9. APPENDICES

Appendix 1. Summary of Clinical Efficacy Analyses

Clinical Efficacy Endpoints	Analysis Set	Baseline	Analysis Method	Missing Data Imputation	Primary Analysis for Primary Endpoint
Loss of Response	FAS-RA	Randomization Date	Time to Event	CAR	Yes
Loss of Response	PPAS	Randomization Date	Time to Event	CAR	No
Loss of Response	FAS-RA	Randomization Date	Time to Event	CNAR	No
Loss of Response based on the IGA score	FAS-RA	Randomization Date	Time to Event	CAR	
Loss of Response based on the IGA score	PPAS	Randomization Date	Time to Event	CAR	
Weeks 2, 4, 8 and 12 IGA Response	FAS-OL	Study	Normal approx.	NR	
Weeks 12, 16, 28, 40 and 52 IGA Response	FAS-RA	Study	CMH and Normal approx.	NR	
Rescue Weeks 2, 4, 8 and 12 IGA Response	FAS-RE	Study	Normal approx.	NR	
Weeks 12, 16, 28, 40 and 52 EASI-50 Response	FAS-RA	Study	CMH and Normal approx.	NR	
Weeks 2, 4, 8 and 12 EASI-75 Response	FAS-OL	Study	Normal approx.	NR	
Weeks 12, 16, 28, 40 and 52 EASI-75 Response	FAS-RA	Study	CMH and Normal approx.	NR	
Rescue Weeks 2, 4, 8 and 12 EASI-75 Response	FAS-RE	Study	Normal approx.	NR	
Weeks 12, 16, 28, 40 and 52 EASI-90 Response	FAS-RA	Study	CMH and Normal approx.	NR	
Weeks 2, 4, 8 and 12 NRS4 Severity Response	FAS-OL	Study	Normal approx.	NR	
Weeks 12, 16, 28, 40 and 52 NRS4 Severity Response	FAS-RA	Study	CMH and Normal approx.	NR	
Rescue Weeks 2, 4, 8 and 12 NRS4 Severity Response	FAS-RE	Study	Normal approx.	NR	
Weeks 12, 16, 28, 40 and 52 SCORAD50 Response	FAS-RA	Study	CMH and Normal approx.	NR	
Rescue Weeks 2, 4, 8 and 12 SCORAD50 Response	FAS-RE	Study	Normal approx.	NR	
Weeks 12, 16, 28, 40 and 52 SCORAD75 Response	FAS-RA	Study	CMH and Normal approx.	NR	
Rescue Weeks 2, 4, 8 and 12 SCORAD75 Response	FAS-RE	Study	Normal approx.	NR	
Weeks 12, 16, 28, 40 and 52 CFBL in Total EASI Score	FAS-RA	Randomization	MMRM	OD	
Rescue Weeks 2, 4, 8 and 12 PCFBL in Total EASI Score	FAS-RE	Rescue	MMRM	OD	
Weeks 12, 16, 28, 40 and 52 CFBL in Total SCORAD Score	FAS-RA	Randomization	MMRM	OD	
Rescue Weeks 2, 4, 8 and 12 PCFBL in Total SCORAD Score	FAS-RE	Rescue	MMRM	OD	
Weeks 12, 16, 28, 40 and 52 CFBL in NRS Score for Severity	FAS-RA	Randomization	MMRM	OD	
Rescue Weeks 2, 4, 8 and 12 CFBL in NRS Score for Severity	FAS-RE	Rescue	MMRM	OD	
Weeks 12, 16, 28, 40 and 52 CFBL in Percent BSA	FAS-RA	Randomization	MMRM	OD	
Rescue Weeks 2, 4, 8 and 12 PCFBL in Percent BSA	FAS-RE	Rescue	MMRM	OD	

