CFBL=Change from baseline; PCFBL=Percent change from baseline; CMH=Cochran-Mantel-Haenszel; MMRM=Mixed-effect Model Repeated Measures; NR=Non-Responder; OD=Observed Data; CAR=Censoring at Random; CNAR=Censoring not at Random

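### The per-protocol set demands study completion only from subjects who did not flare, so membership depends on the outcome and unflared early stoppers are dropped rather than censored

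*SAP*

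**What the plan says.** SAP 4.2 builds the PPAS from FAS-RA by a list of conditions. One is that the subject "if not flared), completed the study". A flared subject faces no completion test.

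Elsewhere the plan censors people who leave without an event:

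- Protocol 9.2.3, which also names the PPAS as the secondary analysis, says that subjects who "discontinue the study during the double-blind randomized period will have their time to event censored at their last known visit in this period".
- SAP 5.2.4 treats permanent discontinuation without an event as a missing event time and refers to SAP 5.3.3. There, for the primary analysis, "these missing event times will be considered as right censored (censored at random) on their last date of dosing".
- SAP 6.1.1.2 and 6.2.1.2 send the PPAS analyses of both endpoints to SAP 5.2.4.
- SAP Appendix 1 gives CAR as the missing-data rule for the PPAS rows of both the primary endpoint and "Loss of Response based on the IGA score". Its key reads "CAR=Censoring at Random; CNAR=Censoring not at Random".

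Protocol 9.2.1 does not name non-completion among the major violations that remove a subject from the PPAS. The SAP adds it.

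**The concern.** Exempting flared subjects is understandable, because they leave blinded treatment for rescue. The fault is requiring completion of everyone else. Two subjects may stop at the same week; the one who flared first stays in the set and the one who did not is deleted. Selection therefore depends on the outcome being analysed. For the primary endpoint, if completion means reaching Week 52, no unflared early stopper is left for the CAR rule to act on.

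The PPAS is one of two supportive analyses of the primary endpoint (SAP 6.1.1.2) and the only one listed for the key secondary endpoint (SAP 6.2.1.2). Part of any gap between PPAS and FAS-RA would come from this rule and could be misread as an effect of adherence.

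**Working it through.** **The plan's own figure.** The plan gives no number for the PPAS. Its only related figure is 94% power for a ratio of medians of 1.5 with 200 per arm at two-sided 5% (protocol 9.1). Schoenfeld's formula gives 4(1.960 + 1.555)²/(ln 1.5)² ≈ 301 events of 400. With exponential times, 40 weeks and no dropout, that corresponds to a placebo median of about 16 weeks. The documents state neither an event count nor a median, so 94% is plausible but not derivable. It is not in dispute.

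**Direction, primary endpoint.** Deleting an unflared stopper takes one event-free subject out of the risk set at every flare before the stop. Each Kaplan-Meier factor 1 − d/n at those times falls. The PPAS flare probability is therefore never below the censored one, and is above it once any flare in the arm precedes such a stop.

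**Size, independent dropout.** All rates are assumed; completion is read as reaching Week 52 (40 blinded weeks). Let a = −ln(1 − p_flare)/40 and d = −ln(1 − p_drop)/40. Then:

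- Completes unflared: S = exp(−40(a + d))
- Flares first: F = a/(a + d) × (1 − S)
- Stops unflared and is deleted: D = d/(a + d) × (1 − S)
- PPAS flare probability: F/(F + S), because nobody in the set is censored early

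For 40% flare and 20% dropout: a = 0.01277, d = 0.00558, S = 0.480, F = 0.362, D = 0.158 (32 of 200). PPAS = 0.362/0.842 = 43.0%.

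| True flare | Dropout 10% | 20% | 30% |
|---|---|---|---|
| 20% | 20.9% | 22.0% | 23.2% |
| 40% | 41.4% | 43.0% | 44.8% |
| 60% | 61.5% | 63.1% | 64.9% |

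In the 40% row, 16, 32 and 48 of 200 per arm are deleted.

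**Size, informative dropout.** Subjects worsen (30, 50 or 70% by 40 weeks), then either flare (mean 8 or 16 weeks) or stop (mean 20 or 40 weeks). In all nine settings censored < PPAS < truth, with PPAS 0.5 to 5.5 points above censored. Example: truth 42.1%, censored 34.4%, PPAS 36.5%.

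**Hazard ratio.** Cox model, 400,000 simulated subjects per arm, placebo flare 40 to 80%, simulation error about 0.01. The true values are 1.00 and 0.667 = 1/1.5.

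| Dropout placebo/active | True 1.00 becomes | True 0.667 becomes |
|---|---|---|
| Equal, 10–30% | about 1.00 | 0.67–0.68 |
| 15% / 10% | 0.97–0.98 | – |
| 20% / 10% | 0.94–0.96 | 0.63–0.64 |
| 10% / 20% | 1.04–1.06 | 0.70–0.71 |
| 30% / 10% | 0.89–0.91 | – |
| 10% / 30% | 1.10–1.13 | – |

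The bias runs against the arm with more unflared stoppers. At the trial's size (200 per arm, placebo median about 16 weeks), suppose 5% on placebo and 15% on active are observed to stop unflared. A true 0.667 is then estimated as 0.72 and power is 76%, against 91% with censoring. Under the null, the rejection rate is 12.2%, against 5.3%.

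**Key secondary endpoint.** Selection is on flare, but the event is IGA ≥2. Under protocol 5.2, a subject with IGA ≥2 who does not meet the flare definition continues blinded treatment. If that subject later stops, an observed event is discarded. Settings: true 60%, base dropout hazard equal to 20% by Week 52, mean lag from IGA ≥2 to flare 5 to 40 weeks, dropout hazard multiplied by 1 to 3 after IGA ≥2. Over 12 settings the PPAS gives 56.7 to 62.5%; the censored set gives 59.9 to 60.0%. The rule deletes 14.7 to 26.1% of subjects, of whom 9 to 49% had already had the event. The two errors can nearly cancel: 59.8% with a 20-week lag and doubled hazard.

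**The case against.** **The term is undefined.** The SAP does not say what completing the study means. Protocol 6.6 keeps subjects who stop treatment in the study for an end-of-treatment visit and four weeks of follow-up. Read loosely, some would count as completers, stay in the PPAS and be censored. This stands as a limit on size: the affected group could be much smaller than simulated. Membership would still depend on outcome for those who leave the study altogether.

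**There is no strict contradiction.** Membership is decided first and censoring applied afterwards, the sentence in SAP 5.3.3 is about the primary analysis, and the protocol lets the SAP modify it and the clinical team define further violations. All true. But SAP 6.1.1.2 and 6.2.1.2 route the PPAS through SAP 5.2.4 to that rule, and Appendix 1 lists CAR for the PPAS rows explicitly.

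**Under informative dropout the present rule can be nearer the truth.** It was, for arm-level flare probabilities, in all nine settings above. That does not carry over to the treatment comparison: in six informative-dropout scenarios the censored hazard ratio was closer to truth each time (for example truth 0.453, censored 0.438, deletion rule 0.398). For the primary endpoint the planned tool is the FAS-RA sensitivity analysis: "Missing time to loss of response will be multiply imputed under censoring not at random under a tipping point analysis framework".

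**The key secondary simulation favours censoring by construction.** Dropout depended on IGA ≥2 only after it occurred, so censoring before the event was uninformative. With informative stopping before the event, which approach is closer depends on the mechanism. This stands, and no tipping-point analysis is planned for that endpoint.

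**Every per-protocol set selects on behaviour after randomization.** True, and selection through compliance and prohibited therapy would remain. Selection directly on the endpoint is a further step, and a time-to-event analysis does not need it.

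**Conclusion.** The concern holds. PPAS membership depends on the primary outcome, and the rule removes subjects whom the rest of the plan would censor. If dropout is independent of flare risk, the PPAS overstates flare probability, by about 1 to 5 points for dropout of 10 to 30%. If worsening subjects tend to stop, it can lie below the truth while still above the censored estimate. The hazard ratio is nearly unchanged with equal dropout and shifts when dropout differs by arm. For the key secondary endpoint the direction is not fixed and the net bias can be near zero.

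All sizes rest on assumed rates, mostly exponential times, and completion read as reaching Week 52. The effect is confined to supportive analyses, so this should be corrected but does not threaten the trial's main conclusions.

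**What to change.** Before unblinding, delete the completion line from SAP 4.2. Keep unflared early stoppers in the PPAS, subject to the other criteria, and censor them as in SAP 5.3.3, which is what Appendix 1 already lists. Add one sentence stating that the 80% to 120% compliance criterion is calculated over time on randomized treatment; with the full 40 weeks as denominator, the same subjects could be excluded again. Informative stopping on the primary endpoint stays with the tipping-point analysis in FAS-RA.

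The cost is one deleted line and one added sentence, with no new data or tests. The PPAS would then include incomplete follow-up and rely on censoring at random, as FAS-RA does. Under informative dropout its arm-level estimates can be further from the truth than under the present rule. Both listed analyses of the key secondary endpoint would rest on that same assumption.

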4.3. Safety Analysis Set (SAF)

In accordance with the FAS, the following groups of SAF will be defined:

SAF-OL: This is the set of all subjects who received at least one dose of study treatment during the open label run-in phase and is the same as FAS-OL. Note that this includes all subjects from the entire study who have received at least one dose of study treatment. For all analyses, Study Baseline will be used (see [Section 3.4](#)).

SAF-RA: This is the set of all subjects who have been randomized at Week 12 and have received at least one dose of study treatment within the double-blind phase. By study design, this will be a subset of SAF-OL. Subjects are classified according to actual study treatment received. In general, for analysis purposes, Study Baseline will be used (see [Section 3.4](#)).

SAF-RE: This is the set of all subjects who have met the protocol definition of a flare (see [Section 2.2](#)) during the double-blind phase and have received at least one dose of rescue treatment. In general, for analysis purposes, Rescue Baseline will be used (see [Section 3.4](#)).

The safety analysis set is the primary population for treatment administration/compliance and safety.

5. GENERAL METHODOLOGY AND CONVENTIONS

The final analysis and reporting of results will be performed after the completion of the study and the database is locked.

5.1. Hypotheses and Decision Rules

The statistical objective of the study is to characterize the loss of response within each randomized group after achieving response at Week 12 following open-label treatment with 200 mg QD PF-04965842.

There are six key hypotheses to be tested for each pairwise comparison between two PF-04965842 doses (200 mg QD and 100 mg QD) and placebo, for the primary and key secondary endpoints. For these hypotheses, the familywise Type-I error rate will be strongly controlled at 5% using a sequential, gatekeeping procedure.

The procedure will first test the hypothesis of no difference for the primary endpoint between 200 mg QD and placebo at 5% level of significance. If this hypothesis is rejected, statistical significance will be assessed for the hypothesis of no difference for the key secondary endpoint between 200 mg QD and placebo at 5% level of significance. If rejected, the procedure will continue with the hypothesis of no difference for the primary endpoint between 100 mg QD and placebo and if rejected, continuing with the hypothesis of no difference between 100 mg QD and placebo for the key secondary endpoint. Finally, if all the above hypotheses are rejected, the procedure will continue with the hypothesis of no difference between 200 mg QD and 100 mg QD for the primary endpoint and if rejected, continuing with the hypothesis of no difference between 200 mg QD and 100 mg QD for the key secondary endpoint. All tests will be conducted at 5% level of significance. Formal statistical significance for any subsequent tests specified in this test hierarchy will not be claimed if the previous hypothesis in the sequence has not been rejected.

Hypotheses for all other endpoints not described here are to be tested at the nominal 5% level, without making adjustments for multiple comparisons.

5.2. General Methods

In general, for descriptive analyses, number and percent will be presented for binary endpoints. Number, median, Q1 and Q3 will be presented for descriptive analyses of continuous efficacy endpoints.

For each of the analysis methods below, treatment comparisons will only be displayed for the FAS-RA analysis set where it is relevant. Pairwise comparisons will be reported among the treatment groups. No treatment comparisons are relevant for the FAS-OL and FAS-RE analysis sets.

